4.5.4.1.1 Adverse Event Definitions

- A. Adverse Event (AE) Any untoward medical occurrence, unintended disease or injury or any untoward clinical signs (including a clinically significant abnormal laboratory finding) in subjects, users or other persons whether or not related to the Sonata System.
 - 1) This includes events related to the procedures involved.
 - 2) For users or other persons this is restricted to events related to the Sonata System or it's procedure
 - 3) Increase in frequency or severity of symptoms relative to baseline are considered an adverse event if they are not related to a measured endpoint
- NOTE 1: An elective surgical reintervention for HMB is not considered an adverse event.
- NOTE 2: Presence of adhesions discovered during follow-up are not considered as an adverse event
- NOTE 3: Inpatient admission does not constitute hospitalization for the purposes of this protocol as long as there are no reported adverse events associated with the stay

B. **Serious Adverse Event (SAE)** – Adverse Event that led to

- 1) Death
- 2) A serious deterioration in the health of the subject that either resulted in:
 - A life-threatening illness or injury, or
 - A permanent impairment of a body structure or a body function, or
 - An in-patient hospitalization, or prolongation of existing hospitalization, of more than 24 hours, or
 - A medical or surgical intervention to prevent life threatening illness or injury or permanent impairment to a body structure or a body function.
- 3) Fetal distress, fetal death or congenital abnormality or birth defect

NOTE 1: A planned hospitalization for a pre-existing condition, or a procedure required by the clinical investigational plan, without a serious deterioration in health, is not considered to be a serious adverse event.

NOTE 2: If recovery time from treatment with the Sonata System is no longer than expected and site scheduling prevents same-day discharge, overnight stay is not considered prolonged

- C. **Adverse Device Effect (ADE)** Adverse Event related to the use of a medical device. This includes:
 - 1) Any adverse event resulting from insufficiencies or inadequacies in the instructions for use, the deployment, the installation, the operation, or any malfunction of the Sonata System.
 - 2) This definition includes any event that is a result of a use error or intentional misuse.

D. Device Deficiency

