4.5.4.1.2 Adverse Event Evaluations

Each adverse event in the study will be evaluated by the investigator as to its severity, its relationship to the study device and to the procedure, and whether it was anticipated in the investigational plan. The distinction between an AE, an SAE, and a UADE will be made according to the definitions given above. Gynesonics is responsible for the classification of adverse events. In case of disagreements in which the investigator's evaluation is that the event is more serious and/or more related, both opinions will be included in adverse event reports.

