4.5.4.1.3 Relatedness

The determination of the level of relatedness of the adverse event to the Sonata device or Sonata procedure will be made according to the definitions below. Adverse events considered to be "Related", "Possibly Related", or "Not Related" to the Sonata System will be classified as an ADE or an SADE for purposes of statistical analysis.

- 1) Related: The adverse event was directly and clearly related to the Sonata System or procedure.
- 2) Possibly Related: The adverse event may have been related to Sonata System or procedure, but an alternative cause is equally likely.
- 3) Not Related: The adverse event was not related to the Sonata System or procedure.

Complications of procedures in the study are considered not related if the said procedures would have been applied to the subject also in the absence of the study device use/application.

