4.6.7 Safety Analyses

4.6.7.1 Adverse Events

Procedure safety will be assessed by recording all AEs that occur on the day of the treatment procedure. Longer-term safety will be assessed by recording at the follow-up visit any untoward medical occurrence since baseline. Each AE will be assessed for relationship to study device and/or procedure. In addition to evaluating procedural and longer-term safety, subjects who become pregnant after the procedure will be asked to report any pregnancy complications.

Descriptions of AEs will include the date of onset, the date the AE resolved, stabilized, or returned to baseline, and the outcome. All reported AEs will be summarized by the number of subjects reporting AEs, seriousness, and relationship to the Sonata System device and/or procedure. Summaries will also be presented for device-related AEs, and procedure-related AEs.

AEs will be summarized both by subject incidence rate and event incidence rate. In addition, AEs will be summarized by relationship to the Sonata System procedure and/or device, such that each subject will be counted only once for each AE by using the AE with the greatest relationship within each category. The sponsor is responsible for classifications of adverse events. Both investigator reported and sponsor evaluated classifications will be summarized.

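### The relatedness levels are defined jointly for device and procedure, while the SAP calls for a separate assessment and a separate summary of each

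*SAP*

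**What the plan says.** Three parts of the SAP treat device and procedure as two things.

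- Section 4.5.4.1.2 has the investigator evaluate each adverse event for "its relationship to the study device and to the procedure".
- Section 4.6.7.1 states "Each AE will be assessed for relationship to study device and/or procedure" and adds "Summaries will also be presented for device-related AEs, and procedure-related AEs".
- Section 4.5.4.1.1, definition C, describes an adverse device effect as "Adverse Event related to the use of a medical device", without naming the procedure as such.

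Section 4.5.4.1.3, which supplies the definitions, pools them. Its lead-in speaks of "The determination of the level of relatedness of the adverse event to the Sonata device or Sonata procedure" without saying whether one rating or two are made. The levels then read:

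- Related: "The adverse event was directly and clearly related to the Sonata System or procedure".
- Possibly Related: "The adverse event may have been related to Sonata System or procedure, but an alternative cause is equally likely".
- Not Related: "The adverse event was not related to the Sonata System or procedure".

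The same section says which levels count as an ADE or SADE. It lists all three, Not Related included, and refers to the Sonata System only.

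**The concern.** A definition has to match the question the rater is asked. Here the question comes in two parts and the definition in one. A rater asked about the device, with an event in hand that arose only from the procedure, finds that the event satisfies the wording of Related. The same happens in reverse. Two fields on the adverse event form would not cure this if both are completed from the stated wording.

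The device-related summary is a main device-safety output of a post-market study. If raters follow the text, it takes in procedure-only events, and the procedure-related summary takes in device-only events. If some raters follow the text and others make the distinction unprompted, the tables mix two definitions. Section 4.6.7.1 reports both investigator and sponsor classifications, so a difference between them could come from the wording alone. The rule in that section of counting each subject once, at the greatest relationship, inherits the same ambiguity.

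**Working it through.** The SAP states no figure that depends on these definitions, so there is none to reproduce. The check is logical.

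**Step 1: two readings of the levels.** Under the literal reading, an event is Related on either rating if it is related to the device or to the procedure, and Not Related only if it is related to neither. Under the shared-scale reading, the rater puts the device in the sentence for one rating and the procedure for the other.

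| True source of the event | Literal: device rating | Literal: procedure rating | Shared scale: device rating | Shared scale: procedure rating |
|---|---|---|---|---|
| Device only | Related | Related | Related | Not Related |
| Procedure only | Related | Related | Not Related | Related |
| Both | Related | Related | Related | Related |
| Neither | Not Related | Not Related | Not Related | Not Related |

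Possibly Related behaves as Related does, because its wording is pooled in the same way.

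**Step 2: what each table counts.** Let d, p, b and n be the numbers of events due to the device only, the procedure only, both, and neither.

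- Literal: device-related = d + p + b, and procedure-related = d + p + b. The tables are identical.
- Shared scale: device-related = d + b, and procedure-related = p + b.
- Difference between readings: (d + p + b) − (d + b) = p in the device table, and (d + p + b) − (p + b) = d in the procedure table.

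The SAP gives none of d, p, b or n. If all related events had both sources (d = p = 0), the readings would agree exactly. If there were little overlap, they would differ widely. No factor can be derived.

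**Step 3: does the rest of section 4.5.4.1.3 resolve it?** Its closing sentence treats as unrelated the complications of procedures that the subject would have had even without the device. That removes some events, such as those from care that would have been given anyway. The Sonata procedure does not take place without the device, so its own complications stay inside the pooled definition.

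**Step 4: the ADE/SADE count.**

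- As written, all three levels count, so ADE = d + p + b + n, which is every adverse event, on either reading.
- With Not Related removed but the levels still pooled: d + p + b on the literal reading, d + b on the shared scale.
- With Not Related removed and the device rating defined separately: d + b.

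The inclusion of Not Related events governs the count as it stands. Once that is corrected, the pooled wording would still let p procedure-only events in on the literal reading. Both corrections are needed for agreement with definition C.

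**The case against.** The best reply is that two ratings were plainly intended. Section 4.5.4.1.2 names two objects, section 4.6.7.1 plans a summary for each, and the lead-in to section 4.5.4.1.3 can be read as introducing one scale for use on either. Many raters would apply it that way. The adverse event form is not shown, so it cannot be established whether one rating or two were collected. This stands, and it limits the point: the tables fail to separate the two sources only where the wording is applied literally. It does not remove the point, because a rater who makes the distinction is using a rule the SAP does not state.

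Definition C also covers deployment, operation and use error, so some events arising during the procedure are properly ADEs. That is right, and a clean division of every event into device or procedure should not be expected. It bears on how large b may be, not on whether the levels need an object.

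The consequence is limited too. The study is exploratory and unpowered, the safety summaries are descriptive, no decision rule uses the split, and adhesions found at follow-up are not counted as adverse events. That stands as well.

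A reader might infer more: that the two tables cannot distinguish device from procedure at all, that the device-related count is inflated by some multiple, or that the pooled levels are what inflates the ADE count. The documents do not support these. The first ignores the two-object wording in sections 4.5.4.1.2 and 4.6.7.1. The second needs event counts and an overlap that the SAP does not give. The third overlooks that the counting sentence already admits every adverse event, however the levels are worded.

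**Conclusion.** The definitions in section 4.5.4.1.3 do not match the separate assessments in section 4.5.4.1.2 or the separate summaries in section 4.6.7.1. Read literally, they make the device rating and the procedure rating the same. Read as a shared scale, they do not. The content of the two tables thus rests on an interpretation that the SAP leaves to each rater. The size is unknown and no inflation factor should be quoted. The conclusion assumes only that raters work from the stated wording, since the adverse event form and any rater instructions are not shown. Separately, the ADE/SADE counting sentence contradicts definition C, because it classes Not Related events as device effects. Both faults concern descriptive safety tables and leave the primary endpoint untouched. They are worth correcting because the SAP states a rule that does not fit its own outputs and the correction costs little.

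**What to change.** In section 4.5.4.1.3, state Related, Possibly Related and Not Related once with the Sonata device as the object and once with the Sonata procedure as the object. Require the investigator and the sponsor each to give both ratings. In section 4.6.7.1, derive the device-related summary from the device rating and the procedure-related summary from the procedure rating, and apply the greatest-relationship rule within each.

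In the same edit, bring the ADE/SADE counting sentence into line with definition C in section 4.5.4.1.1: count only events rated Related or Possibly Related on the device rating. Splitting the levels without this change would leave every adverse event counted as an ADE.

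The cost is a rewording. If only one relatedness field was collected, the sponsor, who is already responsible for classification, would also have to re-rate the adverse events in up to 60 subjects. No change to the primary analysis or the sample size follows.

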4.5.4.2 EuroQOL EQ-5D

The EQ-5D should be completed during the subject's baseline and six week follow-up visit. It should be completed based solely on symptoms from that cycle. If the subject has become amenorrheic, the EQ-5D may be completed at any time during the follow-up visit window. A copy of the questionnaire is included as Appendix B.

4.5.4.3 Treatment Recovery Questionnaire

Subjects will be given a Treatment Recovery Diary at discharge and asked to complete questions daily regarding return to normal activities for the first two weeks post-procedure. A copy of the questionnaire is included as Appendix A.

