4.5.3 Procedure Variables

Procedure information will be captured within the eCRF. The device insertion and removal times will be collected to facilitate the calculation of procedure time. Additionally, the time and date of discharge will be collected. The anesthesia and procedure-related medications, and number and size of each fibroid treated will also be captured, along with the number of ablations for each fibroid.

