4.6.7.3 Treatment Recovery Diary

The treatment recovery diary will be used to calculate the following parameters in days:

- Return to Normal Daily Activities
- Return to Normal Diet
- Return to Normal Sleep
- Return to Normal Urinary Function
- Return to Normal Bowel Movement

Each of these parameters will be summarized using descriptive statistics.

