Appendix A: Treatment Recovery Diary

OP		V	S	TU	DY
Evaluati O n o					
Subject ID:	a mano	COLATOR	-		TIDIOIG

Treatment Recovery Questionnaire Post-Treatment Week 1

1 of 3

The attached questionnaire includes questions about your ability to perform your usual activities.

Please answer these questions every night before going to bed for 14 days following your treatment, and consider the previous 24 hours when answering the questions for each day. Try to answer these questions at the same time every night.

Treatment Day is "Day 0": _____ / ____ / ____ (mm/dd/yy)

	Day 0	Day 1	Day 2	Day 3	Day 4	Day 5	Day 6
1. DATE (mm/dd/yy (ie.,03/24/14))							
2. Were you able to return to normal daily activities today?	Y / N	Y / N	Y / N	Y / N	Y / N	Y / N	Y / N
SPECIFIC ACTIVITIES							
3. Have you returned to work?	Y / N	Y/N	Y / N	Y / N	Y / N	Y / N	Y/N
	Not applicable						
4. Are you able to perform usual household tasks?	Y/N	Y/N	Y/N	Y / N	Y/N	Y/N	Y / N
5. Are you able to drive a car today (even if you did not)?	Y / N	Y / N	Y / N	Y / N	Y / N	Y / N	Y / N
6. Are you able to participate in your usual recreational activities?	Y / N	Y / N	Y / N	Y / N	Y / N	Y / N	Y/N
7. Are you able to lift or carry as normal?	Y / N	Y / N	Y / N	Y / N	Y / N	Y / N	Y / N
8. Are you able to eat your regular diet?	Y / N	Y / N	Y / N	Y / N	Y / N	Y / N	Y/N
9. Are you able to sleep normally?	Y / N	Y/N	Y / N	Y/N	Y / N	Y / N	Y / N
10. Are you able to urinate normally?	Y / N	Y / N	Y / N	Y / N	Y / N	Y / N	Y / N
11. Are you able to have normal bowel movements?	Y/N	Y/N	Y / N	Y / N	Y / N	Y / N	Y/N

CL 04897-013.A 25 May 2017 DCO 5860

CONFIDENTIAL

Treatment Recovery Questionnaire Post-Treatment Week 2

2 of 3

Please enter the date of Day 7 below:

		Day 7	Day 8	Day 9	Day 10	Day 11	Day 12	Day 13
1.	DATE (mm/dd/yy, (ie.,03/31/14))							
2.	Were you able to return to normal daily activities today?	Y / N	Y / N	Y / N	Y / N	Y / N	Y / N	Y / N
	SPECIFIC ACTIVITIES							
3.	Have you returned to work?	Y / N Not applicable						
4.	Are you able to perform usual household tasks?	Y/N	Y / N	Y / N	Y / N	Y / N	Y / N	Y / N
5.	Are you able to drive a car today (even if you did not)?	Y / N Not applicable						
6.	Are you able to participate in your usual recreational activities?	Y/N	Y / N	Y / N	Y / N	Y / N	Y / N	Y / N
7.	Are you able to lift or carry as normal?	Y/N	Y / N	Y / N	Y / N	Y / N	Y / N	Y / N
8.	Are you able to eat your regular diet?	Y / N	Y / N	Y / N	Y / N	Y / N	Y / N	Y / N

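### The recovery diary is handed out at discharge, so a woman kept in hospital overnight cannot make the Day 0 entry that the form asks for that night (minor)

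*SAP*

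**What the plan says.** - **Hand-out.** SAP section 4.5.4.3: "Subjects will be given a Treatment Recovery Diary at discharge and asked to complete questions daily". The diary period is two weeks, counted from the procedure.
- **Completion.** The form in Appendix A instructs: "Please answer these questions every night before going to bed for 14 days following your treatment". It also tells the woman to "consider the previous 24 hours when answering the questions for each day" and to keep to the same time each night. The treatment day is Day 0, and the columns run from Day 0 to Day 13.
- **Overnight stays.** Section 4.5.4.1.1, B, NOTE 2 deals with the case in which "site scheduling prevents same-day discharge, overnight stay is not considered prolonged". A, NOTE 3 of the same section covers inpatient admission without an associated adverse event. Neither gives a frequency.
- **Use of the data.** Section 4.6.7.3: "The treatment recovery diary will be used to calculate the following parameters in days". Five times follow (daily activities, diet, sleep, urinary function, bowel movement), each summarised descriptively. The section does not say which diary entry counts as the return, or how an empty or late-completed column is treated.
- **Missing values and pooling.** Section 4.6.9.2 leaves missing data unimputed unless otherwise specified. Section 4.6.9.4 pools the sites.
- **Discharge.** Under section 4.5.3, "the time and date of discharge will be collected". Section 4.6.5 summarises length of stay.

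**The concern.** The form is designed for same-evening answers, starting on the evening of treatment. Hand-out at discharge defeats that for any woman who spends that night in hospital, because the first entry falls due before she holds the form. NOTE 2 ties the overnight stay to site scheduling rather than to slow recovery, so the gap can follow a site's discharge practice and not the patient's condition.

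What is at stake is how the five recovery times read. For an overnight patient who was already normal on Day 0, the same experience could be scored as 0 days (from recall), as 1 day (first recorded Yes) or as missing, and the SAP does not choose among these.

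**Working it through.** The SAP states no figure for this outcome, so there is nothing to reproduce. The check sets the two instructions side by side and then bounds the possible error.

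**Step 1: the instructions by day of discharge**

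| Discharge | Diary in hand on the night of Day 0? | Day 0 entry as instructed? |
|---|---|---|
| Treatment day | Yes | Possible |
| Day 1 | No | Not possible: blank or recalled |

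The form has 14 columns (Day 0 to Day 13). After one night in hospital, one of the 14 cannot be completed on the evening it refers to.

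**Step 2: effect on one woman**

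Two assumptions are needed, and the SAP states neither: return is the first day marked Yes, and days before hand-out are left blank. Let *k* be the number of nights in hospital. Then

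recorded day = max(true day, *k*), so shift = max(*k* − true day, 0).

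| True return | Shift with *k* = 0 | Shift with *k* = 1 |
|---|---|---|
| Day 0 | 0 | 1 day |
| Day 1 | 0 | 0 |
| Day 2 or later | 0 | 0 |

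Only a return reached before hand-out can be recorded late. With one night that means items already normal on Day 0, by exactly one day.

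**Step 3: effect on the mean**

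Let *f* be the share kept one night and *q* the share of those women truly Yes on Day 0 for the item. The SAP gives neither, so both are varied.

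Mean shift = *f* × *q* × 1 day

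| *f* | *q* = 0 | *q* = 0.25 | *q* = 0.50 | *q* = 0.75 | *q* = 1 |
|---|---|---|---|---|---|
| 0.10 | 0 | 0.025 | 0.05 | 0.075 | 0.10 |
| 0.50 | 0 | 0.125 | 0.25 | 0.375 | 0.50 |

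For example, 0.50 × 0.50 × 1 = 0.25 day.

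**Step 4: if Day 0 is filled in later**

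A woman given the form on Day 1 can still complete the Day 0 column. If she recalls correctly, the shift is 0. Her entry is then retrospective while that of a same-day patient is contemporaneous, and nothing in the data set marks the difference.

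**The case against.** The strongest reply is that this is a small matter of conduct. Same-day discharge creates no conflict, NOTE 2 is a conditional remark about classifying serious adverse events, and a woman given the form the next day can fill in Day 0 within hours. When a form is handed out is often settled in the protocol or site instructions, which are not at hand. The form is dated 25 May 2017 and the SAP 11 April 2019, so a new sentence cannot change diaries already issued. Discharge date and time are collected, so affected women can be identified.

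Most of this stands, and it limits the point. It does not remove it: section 4.5.4.3 itself fixes the hand-out time, that time conflicts with the form, and no rule says what becomes of the Day 0 entry.

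A reader might infer more than the documents support:

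- *That the SAP expects overnight stays.* It provides for them and gives no rate. It does not describe stays of two nights.
- *That inpatients' recovery is in effect timed from discharge.* Day 0 is the treatment day for everyone. A woman who returns to normal on Day 3 records Day 3 whether she left on Day 0 or Day 1.
- *That the reported minimum is distorted.* The pooled minimum remains 0 as long as one same-day patient answers Yes on Day 0.
- *That the shift is large relative to typical recovery times.* The SAP gives no expected recovery times to compare it with.

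**Conclusion.** The conflict is real and confined to women not discharged on the treatment day. Under a first-Yes derivation with Day 0 left blank, and one night in hospital, the mean of an item is overstated by 0 to 0.10 day if 10% stay and by 0 to 0.50 day if 50% stay. Where in that range it falls depends on how many of those women were already normal on Day 0, so items that few women report as normal that day barely move. Both shares are assumed.

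Severity is minor. The diary times are descriptive results in a single-arm study that section 4.6.8 calls exploratory and unpowered, no comparison depends on them, and the adhesion endpoint is unaffected.

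**What to change.** 1. **Section 4.5.4.3.** State that the diary is given before the procedure, or on the treatment day whether or not the woman is discharged, and that the Day 0 entry is made that evening, in hospital if she is still there. Carry the same sentence into the site instructions.
2. **Section 4.6.7.3, for diaries already handed out after Day 0.** Use the discharge date from section 4.5.3 to flag days before receipt as not recorded contemporaneously, state how flagged entries enter the derivation of the five times, and report how many women are affected.

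The cost is about one sentence in each section and one derived flag. No new visit, form or data item is needed.
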